### 1.3.3.1 Clinical Pharmacology Summary

#### Clinical Pharmacokinetics

Clinical pharmacokinetics obtained from studies in patients with solid tumors (Studies NP27872 and NP28902) or with AML (Study NP28679) treated with idasanutlin who were dosed at between 100 and 3200 mg daily or QW are summarized as follows:

- Half-life ( $t_{1/2}$ ) was ~1 day; the half-life was the same on the weekly schedule as on Day 3 or Day 5 of the daily schedules.
- For AUC values, inpatient variability was <30%, and interpatient variability was ~50%.
- East-Asian ethnicity, age, sex, and concomitant cytarabine treatment did not have an apparent impact on PK exposure.
- The SDP formulation was tested in Studies NP28679 and NP28902, and it appears to be twice more bioavailable than the MBP formulation (see [Figure 5](#)).
- There was no major effect of low-fat and high-fat meals on pharmacokinetics for the SDP formulation to be used in the current study.
- Idasanutlin is 99.99% protein bound; bone marrow exposure is ~70% of its plasma level at steady state. Idasanutlin and its metabolites are mainly excreted via the hepatic route through bile, with minimal (<1%) renal elimination.

**Figure 5 Dose Exposure (AUC) SDP versus MBP Formulations in Patients with AML**

AML = acute myeloid leukemia; AUC = area under the concentration • time curve; BID = twice a day; MBP = microprecipitated bulk powder; QD = once a day; SDP = spray-dried powder.

Notes: Both MBP and SDP formulations showed a linear dependence of AUC on dose.

Based on slopes, AUC24h was approximately twice as high with SDP than with MBP.

Data were derived from the AML Study NP28679 and application was QD for 400 mg/d and BID for • 600 mg/d.

### Clinical Pharmacodynamics

Serum levels of macrophage inhibitory cytokine-1 (MIC-1), a secreted protein that is strongly induced by activated p53 (with the promotor containing two p53 response elements), have been used to assess pharmacodynamic (PD) effects in all clinical studies. Following a single dose, an increase in MIC-1 levels by fold change from baseline (FCBL) was observed. Such correlations between MDM2-antagonist therapeutic level exposure and MIC-1 increase as measured by FCBL was identified in early studies of RO5045337 in liposarcoma ([Ray-Coquard et al. 2012](#)) and have been further validated as a biomarker tracking with therapeutic exposure of the current MDM2-antagonist idasanutlin in AML.

## Drug-Drug Interactions

Idasanutlin is a cytochrome (CYP) 2C8 inhibitor that could affect concomitant CYP2C8 substrates at therapeutic exposure levels; its M4 metabolite is an organic anion-transporting polypeptide (OATP)-1B1/3 transporter inhibitor that may affect concomitant OATP1B1/3 substrates. These are the basis for the prohibited therapy list for the present study (see [Table 10](#), [Table 11](#), and [Table 12](#); Section 4.4.2).

However, idasanutlin is not expected to interact with substrates of deaminases such as cytarabine (no interaction observed with cytarabine in Study NP28679). Analysis of this potential interaction will continue throughout the completion of the ongoing Phase I/Ib study NP28679 in AML.

Only one metabolite RO6802287 (M4) (~25% of parent exposure), *which is inactive*, was identified. This metabolite was generated by CYP3A4 and CYP2C8 at an approximate 50:50 ratio. A strong CYP3A4 inhibitor, posaconazole, had no impact on idasanutlin maximum concentration values ( $C_{max}$ ) but increased AUC values by 32%, which suggests a minimal (no clinically significant) drug-drug interaction (DDI) potential with a single use of a strong/moderate CYP3A4 or CYP2C8 inhibitor (*assuming the same minimal effect, as the two isozymes have the metabolic pathway for idasanutlin*). However, a concomitant second strong/moderate inhibitor of the other CYP pathway (e.g., adding CYP2C8 *inhibition* to CYP3A4 *inhibition*) may increase idasanutlin exposure to a clinically significant level. Because some NHL patients receive strong/moderate CYP3A4 inhibitors for prophylactic or treatment purpose, in this protocol CYP2C8 inhibitors will be prohibited to prevent double-blockade DDI. UGT1A3 may be a major clearing enzyme *for idasanutlin*; its strong inhibitor gemfibrozil is also a CYP2C8 inhibitor that will be excluded from the current study.

As idasanutlin is a substrate for both CYP3A4 and CYP2C8, the known inducers of CYP3A4 and CYP2C8 will also be prohibited from the current study to prevent loss of exposure for idasanutlin.

There is no relevant DDI expected between the two combined drugs (*neither between rituximab and idasanutlin nor between obinutuzumab and idasanutlin*) in the present study. No correlation was apparent between idasanutlin plasma concentration and QTcF.

See the idasanutlin Investigator's Brochure (IB) for additional details on nonclinical and clinical studies.

### 1.3.3.2 Clinical Safety of Idasanutlin Solid Tumors (Studies NP27872 and NP28902)

A total of 160 patients with advanced malignancies (excluding leukemia) received idasanutlin in Study NP27872 (Final Date 2 September 2014; 99 patients) and Study NP28902 (cutoff 5 May 2015; 61 patients). All 99 patients in Study NP27872

experienced at least one adverse event, with diarrhea, nausea, vomiting, decreased appetite, and thrombocytopenia as the most common adverse events. Grade 3•5 adverse events were frequently reported in 63.6% of patients with solid tumors treated with idasanutlin in Study NP27872, most commonly from blood and lymphatic system disorders, gastrointestinal disorders, and metabolism and nutrition disorders System Organ Class (SOC).

*In Study NP28902, 85%•100% of patients in each cohort experienced at least one adverse event. The most common adverse events were diarrhea, nausea, decreased platelet count, vomiting, fatigue, constipation, and decreased appetite. GI events were the most common study drug•related adverse events across all treatment groups and occurred during the days of treatment. The events were reversible and manageable with anti-emetic and anti-diarrheal treatments for subsequent cycles.*

Serious adverse events were reported in 32 of 99 patients in Study NP27872, most commonly thrombocytopenia, febrile neutropenia, neutropenia, anemia, and leukopenia. The most frequently reported serious adverse events in Study NP28902 in 16 of 61 patients were pyrexia, cellulitis, and dehydration. Overall, 7 deaths in Study NP27872 and 3 deaths in Study NP28902 were reported. Of the 7 deaths reported in Study NP27872, 5 were attributed to disease progression, 1 was due to intraabdominal hemorrhage with pulmonary embolism (unrelated), and 1 was due to pulmonary embolism (Phase I category: remotely related). In Study NP28902, the cause of death for 2 patients was attributed to disease progression. The cause of death for the other patient in Study NP28902 was pneumonia aspiration, considered unrelated to study drug.

### **Acute Myeloid Leukemia (Studies NP28679 and GH29914)**

Overall, the current safety profile of Study NP28679 is consistent with findings from other studies in patients with R/R AML treated with cytarabine.

*As of 15 April 2016, all patients in NP28679 (n=122) had experienced at least one adverse event. The most common adverse events across the study groups were from the GI Disorders SOC; in particular, patients experienced diarrhea and nausea, and to a lesser extent, vomiting. These events were also the most common adverse events considered by investigators to be related to study treatment. Serious adverse events occurred in 71 of 122 patients during the study; the most common were infectious and hematologic events. Infectious adverse events were more common for patients with AML compared with patients with solid tumors (Studies NP27872 and NP28902). Of the 25 of the 71 serious adverse events that were considered by investigators to be related to study treatment, the most frequent events were sepsis and febrile neutropenia.*

Overall, there were 27 deaths reported during the study, of which 16 deaths were associated with or resulted from adverse events. Of the 8 deaths considered by investigators to be related to study treatment, the causes of death were identified as

sepsis (3 patients), pneumonia (1 patient), *Clostridium difficile* infection (1 patient), *Scedosporium* infection (1 patient), *neutropenic colitis* (1 patient), and neutropenic sepsis (1 patient).

Although the MTD was not reached in a formal manner for the 56 patients with AML during dose escalation, the clinical experience for patients treated at 800 mg BID was evaluated by investigators as not tolerable for those patients, primarily due to GI adverse events (mainly diarrhea) and bone marrow failure (DLT), and further dose escalations were not recommended. Although there are fewer patients treated with the SDP formulation than with the MBP formulation across all studies (solid tumor and AML), there do not appear to be differences in tolerability and/or collective safety parameters.

The adverse event profile of the SDP formulation of idasanutlin with cutoff date of 25 February 2015 (Part 4) is similar to that of the MBP; see [Appendix 13](#).

*In a Phase Ib/II study (GH29914) in elderly patients with R/R AML, 10 patients have received combination therapy with venetoclax (daily dosing) and idasanutlin (Days 1•5) until the cutoff date of 13 September 2016. Three dosing cohorts have been evaluated to date: 3 patients received 400 mg/200 mg (venetoclax/idasanutlin), 3 patients received 400 mg/400 mg, and 4 patients received 600 mg/200 mg. Of the 10 patients enrolled, 9 patients developed at least one adverse event. Similar to other idasanutlin trials, the most common adverse events were reported from SOC infection and infestations and SOC GI disorders across all study groups. There were no fatal adverse events. One case of a serious Grade 3 DLT of asthenia was reported in the 600 mg/200 mg group and was considered related to study treatment by the investigator.*

## **1.4 STUDY RATIONALE AND BENEFIT-RISK ASSESSMENT**

FL remains an incurable disease with the currently available therapies (see Section 1.1.1). Despite significant therapeutic progress with the use of immunochemotherapy as first-line treatment, most patients will eventually experience disease relapse. Relapses are characterized by increasing refractoriness and decreasing duration of response to subsequent lines of therapy. Thus, new treatments are needed to improve the outcome for these patients.

DLBCL is the most common aggressive NHL (see Section 1.1.2), accounting for approximately 30% of all NHLs diagnosed annually. Despite significant therapeutic progress with the addition of rituximab to chemotherapy for first-line treatment of patients with B-cell NHL, FL and DLBCL remain an area of high medical need in which novel targeted therapies are required to improve patient outcome (see Section 1.1).

*Although monotherapy studies with obinutuzumab or rituximab show good response, the limited CR rates indicate the potential need for a combination with a cytotoxic therapy, or at least one other targeted drug with independent but complementary mechanisms of action (Section 1.2.2.1).*

In a RO5045337 AML/CLL study (NO21279), 20 patients with CLL were treated with the suboptimal version and formulation of the MDM2 inhibitor. The dose ranged from 20 mg/m^2 to 1,920 mg/m^2. In total, 15 patients had stable disease and 1 patient with [REDACTED] achieved a PR and continued on to receive 25 cycles. MDM2 inhibitor single-dose therapy is safe but does not lead to relevant clinical responses in CLL in spite of PD biomarker activity. The idasanutlin MBP formulation was tested in a solid tumor study with 95 patients at different doses and schedules, which led to different MTDs that were dependent on dose and schedule. Three patients with NHL tolerated the treatment well but one DLT occurred as prolonged thrombocytopenia. No differences in safety pattern for patients treated with the 400- and 500-mg Days 1•5 BID MBP formulation could be detected compared with that in the solid tumor patients (see Section 1.3.3.2). The main DLTs were thrombocytopenia and neutropenia.

However, based on the fact that the majority of B-lymphoid malignancies, including NHL and CLL, express wild-type p53 and the complementary mechanisms of action involving increased apoptosis (MDM2 antagonists) or direct cell death (obinutuzumab *or* rituximab), the combination of *MDM2 antagonists and obinutuzumab or rituximab* has the potential for superior efficacy *compared to single-agent treatment* in treating B-lymphoid malignancies. The different mechanisms of action (anti-CD20) and two different “late-merging” apoptosis pathways further reduce likelihood of (early) resistance.

In vivo, the combination of obinutuzumab *or rituximab* with the MDM2 inhibitor idasanutlin resulted in robust combined anti-tumor efficacy in p53 wild-type xenograft models (Z-138 and DoHH). These preclinical data strongly support the investigation of obinutuzumab *or rituximab* and idasanutlin as combination therapy in clinical studies for CLL and follicular NHL and DLBCL (Herting et al. 2014; Herting et al. 2016).

Although there is potential of overlapping toxicity with regard to bone marrow suppression (anemia, neutropenia, and thrombocytopenia; see Table 14) between obinutuzumab *or rituximab* and idasanutlin, the Grade • 3 adverse event rates of hematological toxicities for obinutuzumab *or rituximab* are relatively low and range from 3% to 14% and 1% to 4%, respectively. These overlapping toxicities are readily manageable with growth factors, clinical monitoring, and supportive blood transfusions. Clear guidance on dose reduction and a potential delay plan are in place, despite the low starting dose for idasanutlin.

In summary, Study BH29812 has been designed to explore different doses of idasanutlin in combination with a fixed dose of obinutuzumab *or rituximab* in patients with R/R FL and DLBCL, respectively, with the primary objective to determine the MTD in combination with obinutuzumab *for R/R FL and the MTD in combination with rituximab for R/R DLBCL* and the response rates in addition to safety, pharmacokinetics, and exploratory PD parameters in Phase II. The chemotherapy-free regimen being used seeks to offer more options for patients with R/R NHL and could be the first step to future triple combinations free of conventional cytotoxic drugs.

With the below mentioned risk-minimization measures in place (see Section 5.1), the benefit-risk is considered acceptable for the use of idasanutlin in combination with obinutuzumab *or rituximab* in this Phase Ib/II study (see Table 17, Table 18, Table 19, and Table 20).

## **2. OBJECTIVES AND ENDPOINTS**

This study will evaluate the safety, efficacy, and pharmacokinetics of obinutuzumab in combination with idasanutlin in patients with *R/R FL and rituximab in combination with idasanutlin in patients with R/R DLBCL*. Specific objectives and corresponding endpoints for the study are outlined below.

In this study, “study treatment” refers to the *protocol-mandated treatments under study (i.e., obinutuzumab, idasanutlin, and rituximab)*.

### **2.1 SAFETY OBJECTIVES AND ENDPOINTS**

The safety objectives for this study are as follows:

- To determine the recommended Phase II dose (RP2D) for idasanutlin when given in combination with a fixed dose of obinutuzumab *or rituximab* on the basis of the incidence of DLTs during the *DLT windows (see Section 3.1.2.1)* of study treatment
- To evaluate the safety and tolerability of obinutuzumab *or rituximab* in combination with idasanutlin, including DLTs, on the basis of the following endpoints:

Nature, frequency, severity, and timing of adverse events

Changes in vital signs, electrocardiograms (ECGs), and clinical laboratory results during and following study treatment administration

### **2.2 EFFICACY OBJECTIVES**

The objective will be assessment of response determined on the basis of positron emission tomography and computed tomography (PET-CT) scans or CT scans alone, using Revised Lugano Response Criteria for Malignant Lymphoma (Cheson et al. 2014; see Appendix 5), hereinafter referred to as *modified* Lugano 2014 criteria. Response will be determined by an Independent Review Committee (IRC) and by the investigator.

#### **2.2.1 Primary Efficacy Objective and Endpoint**

The primary efficacy objective for this study is to evaluate the efficacy of obinutuzumab in combination with idasanutlin *in R/R FL and rituximab in combination with idasanutlin in R/R DLBCL* on the basis of the following endpoint within each disease cohort:

- CR at end of induction (EOI), as determined by the IRC on the basis of PET-CT scans

### **2.2.2 Secondary Efficacy Objectives and Endpoints**

The secondary efficacy objective for this study is to evaluate the efficacy of obinutuzumab in combination with idasanutlin *in R/R FL and rituximab in combination with idasanutlin in R/R DLBCL* on the basis of the following endpoints within each disease cohort:

- CR at EOI, as determined by the investigator on the basis of PET-CT scans
- CR at EOI, as determined by the IRC and by the investigator on the basis of CT scans alone
- Objective response (defined as a CR or PR) at EOI, as determined by the IRC and by the investigator on the basis of PET-CT scans
- Objective response (defined as a CR or PR) at EOI, as determined by the IRC and by the investigator on the basis of CT scans alone
- Best response of CR or PR during the study, as determined by the investigator on the basis of CT scans alone

### **2.2.3 Exploratory Efficacy Objective and Endpoints**

The exploratory efficacy objective for this study is to evaluate the long-term efficacy of obinutuzumab in combination with idasanutlin *in R/R FL and rituximab in combination with idasanutlin in R/R DLBCL* on the basis of the following endpoints:

- For patients who have positive PET scans at EOI:
  - CR at 12 months, as determined by the IRC and by the investigator on the basis of PET-CT scans *in patients with FL*
  - CR at end of consolidation (EOC), as determined by the IRC and by the investigator on the basis of PET-CT scans, *in patients with DLBCL (expansion only)*
- PFS
- EFS
- Disease-free survival (DFS)
- OS
- Additional descriptive analysis based on TP53 status will be performed on the following endpoint:
  - CR at EOI, as determined by the IRC on the basis of PET-CT scans

## **2.3 PHARMACOKINETIC OBJECTIVES AND ENDPOINTS**

The PK objectives for this study are as follows:

- To characterize the PK profiles of obinutuzumab *or rituximab* and of idasanutlin and its metabolites (if appropriate) to support dose escalation
- To assess potential PK interactions between idasanutlin and obinutuzumab *or rituximab*

- To explore exposure• effect (including PD, efficacy, and adverse event) relationships

## 2.4 BIOMARKER OBJECTIVES AND ENDPOINTS

The exploratory biomarker objective for this study is to identify non-inherited biomarkers that are predictive of response to study treatment (i.e., predictive biomarkers), are associated with progression to a more severe disease state (i.e., prognostic biomarkers), are associated with acquired resistance to study treatment, are associated with susceptibility to developing adverse events, can provide evidence of study treatment activity, can increase the knowledge and understanding of lymphoma biology or study treatment mechanism of action, or can contribute to improvement of diagnostic assays, on the basis of the following:

- Association between non-inherited biomarkers (listed in Section 4.5.6) and efficacy, safety, and PK endpoints including:

*Non-inherited biomarkers from tumor tissue samples and the corresponding pathology report for retrospective central confirmation of the diagnosis of FL or DLBCL (see Table 13)*

*Non-inherited biomarkers from serum and whole blood:*

MIC-1

Circulating lymphoma cells

Cell-free circulating tumor DNA

Lymphocyte immunophenotyping

## 3. STUDY DESIGN

### 3.1 DESCRIPTION OF STUDY

#### 3.1.1 Overview of Study

This Phase Ib/II, open-label, multicenter, non-randomized, dose-escalation study will evaluate the safety, efficacy, and pharmacokinetics of idasanutlin in combination with obinutuzumab in patients with R/R FL *and rituximab in combination with idasanutlin in R/R DLBCL*. The study will include an initial dose-escalation phase *followed by an expansion phase*. *The dose-escalation phase is designed to determine the RP2D for idasanutlin in combination with obinutuzumab for FL and in combination with rituximab for DLBCL. Dose escalation starts with idasanutlin in combination with obinutuzumab in all patients (FL and DLBCL) until the MTD (Regimen A) (see Section 3.1.2) followed by:*

- *Dose confirmation and potential dose escalation in DLBCL patients for idasanutlin in combination with rituximab to determine the RP2D for this combination.*
- *Dose confirmation and potential dose escalation in FL patients for a different regimen (Regimen B, obinutuzumab given alone in Cycle 1 followed by*

*idasanutlin and obinutuzumab in combination from Cycles 2 to 6) to determine the RP2D for this regimen.*

*RP2D(s) and regimens for FL and DLBCL will be decided at the end of dose-escalation phase, and two different RP2Ds and/or regimens may apply for FL and DLBCL, respectively.*

*In the expansion phase, patients with FL will receive idasanutlin at the RP2D of the selected regimen (A or B) in combination with obinutuzumab, and patients with DLBCL will receive idasanutlin at the RP2D in combination with rituximab.*

[figure not shown]
*Patients with R/R FL enrolled in the dose-escalation phase may be eligible to receive post-induction treatment (referred to as maintenance) with obinutuzumab (see Section 3.1.2.2 and Section 3.1.3 for details on treatment regimens).*

*Patients with R/R FL enrolled in the expansion phase may be eligible to receive maintenance treatment with obinutuzumab and idasanutlin (see Sections 3.1.2.2 and 3.1.3, respectively, for details on the treatment regimens).*

*Patients with R/R DLBCL enrolled in the expansion phase may be eligible to receive post-induction treatment (referred to as consolidation) with rituximab and idasanutlin (see Section 3.1.3 for details on treatment regimens).*

A study schema is provided in [Figure 6](#). Refer to Sections [3.1.2](#) and [3.1.3](#) for details on the treatment regimens.

Figure 6 Study Schema

DLBCL = diffuse large B-cell lymphoma; FL = follicular lymphoma; RP2D = recommended Phase II dose.

Overall, approximately 89• 120 patients with R/R FL and DLBCL are expected to be enrolled in this study at approximately 25 investigative sites around the world.

All patients will be closely monitored for adverse events throughout the study and for at least 90 days after the last study treatment (see Section 5.3.1). Adverse events will be graded according to the National Cancer Institute Common Terminology Criteria for Adverse Events, Version 4.0 (NCI CTCAE, v4.0). An internal monitoring committee (IMC) will be established to monitor patient safety throughout the study (see Section 3.1.4).

Response will be determined by the IRC (see Section 3.1.4) and the investigator using slightly modified Lugano 2014 criteria requiring normal bone marrow for PET-based CR if bone marrow was positive at baseline (see Appendix 5). The primary efficacy endpoint will be based on IRC assessment of response. Refer to Section 4.5.5 for details on tumor assessments.

The schedules of assessments are provided in Appendix 1 and Appendix 2; the schedule for PK assessments is presented in Appendix 3.

### **3.1.2            Dose-Escalation Phase (Part 1)**

The purpose of the dose-escalation phase (Part 1) is to identify the RP2D *and regimen* for idasanutlin when combined with a fixed dose of 1000 mg of obinutuzumab in patients with R/R FL and *the RP2D for idasanutlin when combined with 375 mg/m^2 of rituximab in patients with R/R DLBCL*. The RP2D will be based on MTD of idasanutlin when combined with a fixed dose of obinutuzumab *or with 375 mg/m^2 of rituximab*, but will also include all safety data during treatment. *There could be two different RP2Ds and/or regimens dependent on the combinations of idasanutlin plus obinutuzumab or idasanutlin plus rituximab.*

During the escalation phase, approximately 9• 40 patients will be enrolled in dosing groups of 3• 6 patients each and will be treated at escalating doses of idasanutlin in accordance with the treatment regimen and dose-escalation rules described in Section 3.1.2.2.

Patients will be closely monitored for adverse events during a DLT assessment window, defined as the first treatment cycle *for Regimen A and the first two treatment cycles (one cycle of idasanutlin combination treatment) for patients enrolled in bridging cohort(s) in which idasanutlin will start at Cycle 2 (Regimen B)*. See Section 3.1.2.2 for treatment regimens. Adverse events meeting the criteria for DLT, as defined below (see Section 3.1.2.1), will be reported to the Sponsor within 24 hours (see Section 5.4.2).

Patients experiencing a DLT during the *DLT window* will permanently discontinue study treatment.

Patients who discontinue from the study prior to completing the DLT assessment window for reasons other than a DLT will be considered non-evaluable for dose-escalation decisions and MTD assessments and will be replaced by an additional patient at that same dose level who has not been previously treated in the study. Patients who miss one or more doses of obinutuzumab, *rituximab*, or idasanutlin during the DLT assessment window for reasons other than a DLT will also be replaced.

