### 3.1.2.1 Definition of Dose-Limiting Toxicity

In this study, a DLT is defined as at least one of the following events occurring during the first cycle (*or the first two cycles in the bridging cohorts for patients with FL who start idasanutlin at Cycle 2*) of treatment and assessed by the investigator as not clearly related to the patient's underlying disease:

- *Any Grade 5 adverse event unless unequivocally due to the underlying malignancy or extraneous causes*
- Adverse event of any grade that leads to a delay of more than 14 days in the start of the next treatment cycle
- Grade 3 or 4 non-hematologic adverse event, with the following exceptions:
  - Grade 3 or 4 IRRs
    - Note that IRRs are not dose-dependent events. They may occur even after a small amount of drug has been administered.
    - Grade 3 diarrhea that responds to adequate therapy within 48 hours
    - Grade 3 nausea or vomiting that occurs in the absence of premedication and responds to adequate therapy within 72 hours
- *Any increase in hepatic transaminase > 3 • baseline and an increase in direct bilirubin > 2 • ULN, without any findings of cholestasis or jaundice or signs of hepatic dysfunction and in the absence of other contributory factors (e.g., worsening of metastatic disease or concomitant exposure to known hepatotoxic agent or of a documented infectious etiology) is suggestive of potential drug induced liver injury (according to Hy's Law) and will be considered a DLT*
- Hematologic adverse events that meet any of the following criteria:
  - Grade 3 or 4 neutropenia in the presence of sustained fever of >38°C (lasting >5 days) or a documented infection
  - Grade 4 neutropenia lasting >7 days
  - Grade 3 or 4 thrombocytopenia *if associated with Grade ≥ 3 bleeding*
  - Grade 4 thrombocytopenia lasting >7 days

Other toxicities that are considered clinically relevant and related to study treatment as determined by the investigator and the Medical Monitor may also be considered DLTs.

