### **4.6.2 Study Treatment Discontinuation**

Study treatment (obinutuzumab *or rituximab* and idasanutlin) should be permanently discontinued in patients who experience any of the following:

- DLT during *the DLT window* in patients enrolled in the dose-escalation phase
- Anaphylaxis, acute respiratory distress, or Grade 4 IRR
  - If a Grade 3 IRR is recurrent during the second and subsequent cycles, study treatment may be discontinued at the discretion of the investigator, following an individual benefit• risk assessment.
- Any adverse event that leads to a delay of more than 21 days in the start of the next treatment cycle
- Any hematologic adverse event that meets criteria for permanent discontinuation per guidelines provided in Section 5.1.5
- Grade • 3 non-hematologic adverse event that has a reasonable possibility of being related to study treatment and is either life threatening or does not resolve to Grade <2 within 21 days
- Disease progression
- Pregnancy

The primary reason for study treatment discontinuation should be documented on the appropriate eCRF.

Patients who discontinue study treatment will not be replaced, except as outlined below:

- During the dose-escalation phase (Part 1), patients who discontinue study treatment prior to completing Cycle 1 for reasons other than toxicity will be replaced.
- Patients discontinued before having received at least one dose of each component of the combination will be replaced.

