**Table 18 Guidelines for Management of Hematologic Toxicities That Occur on Days 8 and 15 of Cycle 1**

Event	Action to Be Taken
Febrile neutropenia or neutropenia with infection	
 
• Withhold obinutuzumab until resolution of fever and infection (as applicable).
 
• If the event is ongoing on Day 1 of Cycle 2, follow instructions in Table 17.
 
 
Note: Obinutuzumab should not be withheld for asymptomatic neutropenia.

Severe thrombocytopenia a or bleeding	
 
• Withhold obinutuzumab until platelet count <math>\geq 50,000/\mu\text{L}</math> and resolution of bleeding.
 
• If the event is ongoing at Day 1 of Cycle 2, follow instructions in Table 17.
 

a Severe thrombocytopenia is defined as a platelet count  $< 10,000/\mu\text{L}$  for patients who are not receiving concomitant anticoagulants or platelet inhibitors.

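### Sections 3.1.2 and 4.6.2 give conflicting replacement rules for a Part 1 patient who stops for toxicity short of a DLT, and neither says how that patient enters the mCRM

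*Combined protocol and SAP*

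**What the plan says.** Section 3.1.2 has two sentences on incomplete patients. For patients who withdraw from the study, the rule reads "prior to completing the DLT assessment window for reasons other than a DLT will be considered non-evaluable for dose-escalation decisions and MTD assessments"; they are replaced at the same dose. Those who miss a dose of either antibody or of "idasanutlin during the DLT assessment window for reasons other than a DLT will also be replaced". The term non-evaluable stands only in the first sentence. The window is Cycle 1 for Regimen A and two cycles for Regimen B.

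Section 4.6.2 starts from the opposite default: "Patients who discontinue study treatment will not be replaced, except as outlined below". Its Part 1 exception is that "patients who discontinue study treatment prior to completing Cycle 1 for reasons other than toxicity will be replaced". A second exception replaces anyone who stops before receiving each component at least once.

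Section 3.1.2.1 sets the DLT threshold. For platelets, "Grade 4 thrombocytopenia lasting >7 days" qualifies, as does Grade 3 or 4 with Grade 3 or worse bleeding. Grade 3 or 4 neutropenia with fever but no documented infection qualifies only if the fever lasts more than 5 days. Infusion-related reactions (IRRs) of Grade 3 or 4 are exempt. Other relevant, treatment-related toxicities "as determined by the investigator and the Medical Monitor may also be considered DLTs".

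Section 3.1.2.3 updates the model on observed DLT data and counts DLT-evaluable patients. It does not say how an incomplete patient is handled.

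**The concern.** A dose-finding model can learn only from the patients it is given. If patients whose treatment is interrupted as toxicity emerges are taken out and replaced, the remaining set may be selected for tolerance, and a dose can look safer than it is. The MTD from Regimen A is the starting point for both bridging cohorts, so an error there carries forward.

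The more immediate problem is operational. Sites and sponsor have two instructions for the same patient, so the choice could be made case by case after the toxicity is known.

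**Working it through.** **1. Where the two sections collide.** Take a Regimen A patient with a Grade 4 IRR in Cycle 1.
- Section 4.6.2 stops treatment permanently, and Section 3.1.2.1 exempts the event from the DLT definition.
- Later doses in the window are missed for a reason other than a DLT, so 3.1.2 replaces the patient.
- The reason is a toxicity, so 4.6.2 does not replace. Its second exception should not apply, because Section 4.3.2.2 puts idasanutlin before the infusion and both components have been started.

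The same conflict arises for any other sub-DLT toxicity that leads to stopping in Cycle 1.

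**2. The window.** A Regimen B patient who stops in Cycle 2 after starting idasanutlin, for a reason unrelated to toxicity, is replaced under 3.1.2. Under 4.6.2 the patient is past Cycle 1 and is not. Conversely, a Regimen B patient who leaves in Cycle 1 has had no idasanutlin and is replaced under both.

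**3. Holds.** Section 4.6.2 covers only stopping, so holds cannot contradict it. They show how far 3.1.2 may reach.
- Table 18 holds Day 8 or 15 obinutuzumab for febrile neutropenia or for platelets below 10,000/µL. Neither need be a DLT.
- Table 19 holds treatment for other Grade 2 non-hematologic events.
- Such events are foreseeable: Table 14 reports Grade 3 or worse thrombocytopenia in 44%, neutropenia in 27% and febrile neutropenia in 12% of 34 patients on 5-day single-agent idasanutlin.
- The plan does not say whether a dose given late counts as missed.

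**4. Effect on the observed DLT rate.** Let p be the true rate, q the share removed, and f the share of those removed who would have had a DLT. The evaluable rate is (p − f·q)/(1 − q). Neither q nor f is in the documents; both are assumptions. For p = 35%:

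| q | f = 1 | f = 1/2 | f = p (unrelated) |
|---|---|---|---|
| 5% | 31.6% | 34.2% | 35% |
| 10% | (0.35 − 0.10)/0.90 = 27.8% | (0.35 − 0.05)/0.90 = 33.3% | 35% |
| 15% | 23.5% | 32.4% | 35% |

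If f is below p, the bias reverses: f = 0 with q = 10% gives 0.35/0.90 = 38.9%.

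**5. Effect of one patient on the recommendation.** Inputs from Section 3.1.2.3:
- logit p(d) = log α + β·log(d/300)
- log α ~ N(−1.237, variance 2.661) and log β ~ N(0.460, variance 1.816), independent
- loss 1, 0, 1, 2 for the intervals 0–25, 25–35, 35–60 and 60–100%
- 50-mg steps; 151% increment cap up to 300 mg

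The plan's own figures come first. Choosing the lowest-loss dose from a grid posterior reproduces 14 of the 16 stated recommendations for the first four cohorts (100, 250, 300, 300 mg; 0 to 3 DLTs each). The misses are 3/3 at 250 mg (150 mg against a stated 100 mg) and 0/3 at the second 300-mg cohort (300 against 350 mg). Also enforcing the 35% overdose limit changes three more cells: 2/3 and 3/3 at 100 mg, and 3/3 at the second 300-mg cohort. None of these cells is used below, and the results below are the same with or without that limit.

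After 0/3 at 100 mg, suppose one of three patients at 250 mg is a toxicity-driven non-completer and the others have no DLT:

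| Handling | Data at 250 mg | Next dose | Mean DLT risk at 250 mg | P(risk > 35%) |
|---|---|---|---|---|
| Excluded, not replaced | 0/2 | 300 mg | 10.1% | 0.045 |
| Excluded and replaced, or kept as no DLT | 0/3 | 300 mg | 8.7% | 0.027 |
| Kept as no DLT, one patient added | 0/4 | 300 mg | 7.7% | 0.017 |
| Scored as DLT | 1/3 | 250 mg | 22.6% | 0.203 |
| Scored as DLT, one patient added | 1/4 | 250 mg | 19.5% | 0.138 |

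In the first cohort at 100 mg, 0/3 gives 250 mg, 1/3 gives 100 mg and 1/4 gives 150 mg. Replacement alone does not move the recommendation. Scoring does.

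**The case against.** The plan has safeguards. The investigator and Medical Monitor can call further toxicities DLTs. Each cohort decision reviews adverse event, laboratory and dose-administration data. Clinical judgment overrides the model, and the RP2D takes in all safety data. A dose that many patients cannot complete would be visible. This stands as mitigation, but each safeguard is discretionary and none tells a site or statistician which replacement rule applies.

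A held dose also does not end observation. Idasanutlin is scheduled for Days 1–5, so a Day 8 or 15 antibody hold comes after the course, and a cytopenia that then lasts long enough still becomes a DLT. That is fair, and it weakens the bias argument for Table 18 holds.

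A reader might go further and infer that toxicity-driven non-completers disappear from the mCRM, so that the MTD is biased upward, or that every hold under Tables 18 and 19 contradicts Section 4.6.2. The documents do not support either. Exclusion is written only for study leavers and merely implied for missed doses; the size and direction of any bias depend on f, which is unknown; and 4.6.2 is silent on holds.

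**Conclusion.** The conflict between the two sections is in the current text and needs reconciling, for both the reason (DLT or toxicity) and the window (Cycle 1 or the DLT window). Separately, 3.1.2 leaves open what counts as missed and whether a replaced patient leaves the model data.

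The consequence for the MTD is possible but not quantified. With 10% removed and a true rate of 35%, the observed rate runs from 27.8% (all would have had a DLT) through 33.3% (half) to 35% (removal unrelated to DLT risk). These values rest on assumed q and f. What the plan's own model does show is sensitivity: at 250 mg, scoring one patient as an event or not separates staying at 250 mg from escalating to 300 mg. That warrants a fixed rule before the data are seen.

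**What to change.** Reconcile 3.1.2 and 4.6.2 into one replacement and evaluability rule, stated in terms of the DLT window so that it also fits Regimen B. Define whether a delayed dose is missed. State explicitly how patients who stop or miss doses because of toxicity are handled, so that they are not silently dropped from the dose-finding data.

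At each dose meeting, list these patients and show the mCRM recommendation three ways: with them excluded, scored as no DLT, and scored as DLT. Leave events that the DLT definition exempts, such as IRRs, out of the third run. Simply retaining them as no DLT is not enough, because it lowers the apparent rate relative to exclusion.

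The cost is a text change, extra model runs per cohort, possibly slower escalation, and possibly one added patient in a cohort, because Section 3.1.2.2 requires three patients to complete the window before the next cohort opens.
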